6.3 Contraindicated Medications in the Study

1. The use of rescue medications for non-rescue purposes is prohibited during chemotherapy;
2. During chemotherapy cycles, the use of medications containing rolapitan, palonosetron, or dexamethasone is prohibited except for visits specified in the treatment regimen.
3. The following medications are prohibited during the study period:
 - (1) Specific CYP3A4 substrates: terfenadine, cisapride, astemizole;
 - (2) Strong CYP3A4 inducers: phenobarbital, rifampin, phenytoin, and carbamazepine;

- (3) CYP3A4 inhibitors: ritonavir, clarithromycin, ketoconazole, itraconazole, diltiazem, etc.;
- (4) Specific CYP2D6 substrates: thioridazine, pimozide.

7 Informed Consent

The rights, safety, and physical/mental well-being of participants are paramount considerations, taking precedence over scientific and societal benefits. After explaining the fundamental aspects of the study and confirming participants' understanding of its objectives, investigators must require each participant to sign their name and date on the Informed Consent Form (ICF). Participants should carefully review and consider their informed consent statement before signing, and obtain a signed ICF. Prior to initiating any clinical study-related procedures, a signed ICF must be obtained from participants, including informed consent for any screening processes conducted to determine eligibility for study participation. Participants may not proceed with the study without obtaining informed consent.

For subjects who are unable to sign the informed consent form independently for any reason, the legal guardian must sign on their behalf. The ICF signed by the subject and the investigator with their names and dates must be properly retained by the investigator and documented in the relevant original research records.

The confidentiality of subject information is strictly enforced by investigators, participating researchers, and their agents. Confidentiality also extends to biological samples and genetic testing beyond clinical subject data. Consequently, the study protocol, documentation, data, and all other generated information will be rigorously protected. No relevant study or data information may be disclosed to unauthorized third parties without written approval. The research data entry and management systems utilized by clinical research centers and researchers at the Second Affiliated Hospital of Zhejiang University School of Medicine are password-protected and configured with confidentiality settings. Upon study completion, all identifying information in research databases will be anonymized and archived at the Second Affiliated Hospital of Zhejiang University School of Medicine.

8 Adverse Event Reporting

8.1 Adverse Events

Adverse events (AEs) refer to all adverse medical events occurring in subjects after receiving the investigational drug, which may manifest as symptoms, signs, diseases, or abnormal laboratory findings, but not necessarily have a causal relationship with the investigational drug. AEs include, but are not limited to:

- (1) Worsening of pre-existing medical conditions/diseases (including exacerbation of symptoms, signs, and abnormal laboratory findings) prior to enrollment in clinical trials;
- (2) Any newly occurring adverse event (AE): Any newly occurring adverse medical condition (including symptoms, signs, and newly diagnosed diseases);
- (3) Abnormal laboratory test values or results with clinical significance (known prior to screening

or newly identified during screening as comorbidities or baseline conditions, not recorded as adverse events [AEs]).

8.2 Severity and Criteria for Adverse Events

Refer to the NCI-CTCAE 5.0 version classification criteria for drug adverse events (AEs).

For AEs not listed in the NCI-CTCAE 5.0 table, the following criteria may be applied:

grade	Clinical description of severity
1	Mild: No clinical symptoms or only mild clinical symptoms; only clinical or laboratory abnormalities; no treatment required
2	Moderate: Requires minor, localized, or non-invasive treatment; age-appropriate instrumental activities of daily living (ADLs) are limited, including instrumental daily activities such as cooking, shopping, making phone calls, and counting money.
3	Severe illness or medically significant symptoms that are not immediately life-threatening; leading to hospitalization or prolonged hospital stay; resulting in disability; impairing daily activities of living (Selfcare ADL). Daily activities of living refer to: bathing, dressing, undressing, eating, using the toilet, taking medication, etc., without requiring bed rest.
4	Life-threatening; requires emergency treatment
5	Adverse Events Leading to Death

Abbreviations: AE = adverse event; ADL = activities of daily living.

8.3 Assessment of Causality Between Adverse Events and Investigational Drug

The determination of causality between adverse events (AEs) and investigational drugs involves comprehensive evaluation to assess whether there is a reasonable likelihood that the investigational drug caused or contributed to the AEs. Key factors include whether the AEs occurred in a reasonable temporal sequence relative to drug administration, the characteristics of the investigational drug, its toxicological and pharmacological effects, concomitant medication use, the subject's underlying diseases, medical history, family history, and desensitization/reexposure reactions. Typically, evidence or arguments supporting causality determination should be provided.

The causal relationship between AE and the investigational drug should be assessed by the investigator as "definitely associated", "possibly associated", "possibly unrelated", "definitely unrelated", or "uncertain".

8.4 Serious Adverse Events

A Serious Adverse Event (SAE) is any of the following adverse medical events occurring in a subject after receiving any dose of the investigational drug:

- (1) Leading to death;
- (2) Life-threatening (defined as the subject being at risk of death at the time of event occurrence, without implying that worsening of the condition would necessarily lead to death);
- (3) Requires hospitalization or prolonged hospital stay;

- (4) Permanent or apparent disability/function loss;
- (5) Congenital anomalies/birth defects;
- (6) Other significant medical events.

Appendix I: ECOG Physical Status Score

Prior to treatment, an assessment of the patient's general health status should be conducted. A key indicator of general health status is the evaluation of performance status (PS), which reflects the patient's physical condition and serves as an indicator of their tolerance to treatment. The Eastern Cooperative Oncology Group (ECOG) has developed a simplified performance status scoring system, as shown in the table below:

ECOG Physical Status Score Criteria

Activity Score	description
0	Asymptomatic, with full voluntary movement and the ability to perform unrestricted activities.
1	Symptomatic, fully capable of walking, but with limited capacity for heavy physical activities. Able to perform light or sedentary tasks, such as minor household chores or office work.
2	Symptomatic, able to walk and perform daily activities independently, but unable to engage in any physical activity. Approximately 50% of the time is spent conscious (daytime bed rest <50%).
3	Symptomatic, with limited ability for self-care, bedridden or sitting for >50% of waking hours, but not yet bedridden.
4	Complete loss of function, inability to perform any self-care activities, and bedridden status.
5	die .

Appendix II: Functional Life Impact of Vomiting Scale (FLIE)

The Vomiting Life Impact Scale (FLIE) is a patient-reported questionnaire designed to assess the quality of life affected by nausea and vomiting. The questionnaire consists of 18 questions, divided into two sections: nausea and vomiting, with 9 questions in each section. See the table below for details.

Each question was evaluated using an intuitive simulation scale. Carefully read the questions, as in some items, a "1" indicates no impact on your quality of life, while in others, a "1" signifies a significant impact. The numerical value increases progressively with higher scores, with "7" representing the opposite meaning of the aforementioned "1". Nausea scores, vomiting scores, and total scores were calculated by summing responses across categories and the total number of responses. Scoring was performed before each chemotherapy cycle, 24 hours after chemotherapy, 120 hours after chemotherapy, and 168 hours after chemotherapy.

Participants must draw vertical lines on the intuitive simulation scale when responding. The operational example is as follows:

Vomiting Life Functioning Inventory (FLIE)

1: Have you experienced nausea during the following periods: before chemotherapy/within 1 day after chemotherapy initiation (0-24 hours)/2-5 days after chemotherapy initiation (24-120 hours)/6-7 days after chemotherapy initiation (120-168 hours)?

1	2	3	4	5	6	7
						

Not very large at all

Not very large at all

2: Did your nausea affect your ability to continue normal recreational or leisure activities during the following periods: before chemotherapy/1 day after chemotherapy initiation (0-24 hours)/2-5 days after chemotherapy initiation (24-120 hours)/6-7 days after chemotherapy initiation (120-168 hours)?

1	2	3	4	5	6	7
						

Not very large at all

Not very large at all

3: During the period before chemotherapy/1 day after chemotherapy initiation (0-24 hours)/2-5 days after chemotherapy initiation (24-120 hours)/6-7 days after chemotherapy initiation (120-168 hours), did your nausea affect your ability to prepare a meal or perform light household tasks?

1	2	3	4	5	6	7
						

Very large, not at all

Very large, not at all

4: How much did your nausea affect your ability to eat during the following periods: before chemotherapy/1 day after chemotherapy initiation (0-24 hours)/2-5 days after chemotherapy initiation (24-120 hours)/6-7 days after chemotherapy initiation (120-168 hours)?

1	2	3	4	5	6	7
						

Not very large at all

Not very large at all

5: To what extent does your nausea affect your ability to consume beverages during the following periods: before chemotherapy/1 day after chemotherapy initiation (0-24 hours)/2-5 days after chemotherapy initiation (24-120 hours)/6-7 days after chemotherapy initiation (120-168 hours)?

1	2	3	4	5	6	7
						

Not very large at all

Not very large at all

6: How much does your nausea affect your willingness to visit and spend time with family and friends before chemotherapy, within 1 day after chemotherapy initiation (0-24 hours), within 2-5 days after chemotherapy initiation (24-120 hours), or within 6-7 days after chemotherapy initiation (120-168 hours)?

1	2	3	4	5	6	7
						

Very large, not at all

Very large, not at all

7: Did your nausea affect your daily activities during the following periods: before chemotherapy/1 day after chemotherapy initiation (0-24 hours)/2-5 days after chemotherapy initiation (24-120 hours)/6-7 days after chemotherapy initiation (120-168 hours)?

1	2	3	4	5	6	7
						

Not very large at all

Not very large at all

8: Please evaluate the degree of distress caused by your nausea to you personally during the following periods: within 1 day before chemotherapy/after chemotherapy initiation (0-24 hours), 2-5 days after chemotherapy initiation (24-120 hours), and 6-7 days after chemotherapy initiation (120-168 hours).

1	2	3	4	5	6	7
						

Not very large at all

Not very large at all

9: Please assess the degree of difficulty your nausea has caused to the lives of your closest loved ones during the following periods: within 1 day before chemotherapy/after chemotherapy initiation (0-24 hours), 2-5 days after chemotherapy initiation (24-120 hours), and 6-7 days after chemotherapy initiation (120-168 hours).

1	2	3	4	5	6	7

Not very large at all

Not very large at all

10: Have you experienced vomiting during the following periods: before chemotherapy/within 1 day after chemotherapy initiation (0-24 hours)/2-5 days after chemotherapy initiation (24-120 hours)/6-7 days after chemotherapy initiation (120-168 hours)?

1	2	3	4	5	6	7

Not very large at all

Not very large at all

11: Did vomiting affect your ability to continue normal recreational or leisure activities during the following periods: before chemotherapy/within 1 day after chemotherapy initiation (0-24 hours)/2-5 days after chemotherapy initiation (24-120 hours)/6-7 days after chemotherapy initiation (120-168 hours)?

1	2	3	4	5	6	7

Very large, not at all

Very large, not at all

12: Did your vomiting condition affect your ability to prepare a meal or perform light household tasks during the following periods: before chemotherapy/1 day after chemotherapy initiation (0-24 hours)/2-5 days after chemotherapy initiation (24-120 hours)/6-7 days after chemotherapy initiation (120-168 hours)?

1	2	3	4	5	6	7

Not very large at all

Not very large at all

13: How much did your vomiting affect your ability to eat during the following periods: before chemotherapy/1 day after chemotherapy initiation (0-24 hours)/2-5 days after chemotherapy initiation (24-120 hours)/6-7 days after chemotherapy initiation(120-168 hours)?

1	2	3	4	5	6	7
						

Not very large at all

Not very large at all

14: How much did your vomiting affect your ability to consume beverages during the following periods: before chemotherapy/1 day after chemotherapy initiation (0-24 hours)/2-5 days after chemotherapy initiation (24-120 hours)/6-7 days after chemotherapy initiation(120-168 hours)?

1	2	3	4	5	6	7
						

Not very large at all

Not very large at all

15: How much does your vomiting condition affect your willingness to visit and spend time with family and friends before chemotherapy, within 1 day after chemotherapy initiation (0-24 hours), within 2-5 days after chemotherapy initiation (24-120 hours), or within 6-7 days after chemotherapy initiation (120-168 hours)?

1	2	3	4	5	6	7
						

Very large, not at all

Very large, not at all

16: Did vomiting affect your daily activities during the following periods: before chemotherapy/within 1 day after chemotherapy initiation (0-24 hours)/2-5 days after chemotherapy initiation (24-120 hours)/6-7 days after chemotherapy initiation (120-168 hours)?

1	2	3	4	5	6	7
						

Not very large at all

Not very large at all

17: Please assess the degree of personal distress caused by vomiting during the following periods: within 1 day before chemotherapy/after chemotherapy initiation (0-24 hours), 2-5 days after chemotherapy initiation (24-120 hours), and 6-7 days after chemotherapy initiation (120-168 hours).

1	2	3	4	5	6	7
						

Not very large at all

Not very large at all

18: Please assess the degree of difficulty your vomiting has caused to the lives of your closest loved ones during the following periods: within 1 day before chemotherapy/after chemotherapy initiation (0-24 hours), 2-5 days after chemotherapy initiation (24-120 hours), and 6-7 days after chemotherapy initiation (120-168 hours).

1	2	3	4	5	6	7
						

Very large, not at all

Very large, not at all

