3.5 Study Endpoints

[figure not shown]
Primary efficacy endpoint

The proportion of subjects achieving complete remission (CR: no vomiting and no rescue therapy) with an ultra-long delay period (120 h-168 h) after chemotherapy initiation in each immunotherapy plus chemotherapy cycle.

Secondary efficacy endpoint

- (1) CR rates during the acute phase (0-24 h), delayed phase (24 h-120 h), overall phase (0-120 h), and 0-168 h periods of each immunotherapy + chemotherapy cycle;
- (2) Comparison of the time to first vomiting using Kaplan-Meier curves;
- (3) Assess the impact of chemotherapy-induced nausea and vomiting on quality of life using the Functional Life Index-Vomiting (FLIE);
- (4) Incidence of adverse events and serious adverse reactions throughout the study period, such as safety concerns including prolonged Q-T interval and constipation.

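### Appendix II scores the FLIE as a plain sum of responses although it says item directions differ; as written, opposite items partly offset the rest and the score has no stated direction

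*Protocol*

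**What the plan says.** Section 3.5 of the Protocol lists quality of life, measured by the FLIE, as a secondary efficacy endpoint. Appendix II describes the instrument: "The questionnaire consists of 18 questions, divided into two sections: nausea and vomiting, with 9 questions in each section". Responses run from 1 to 7. The instructions warn that "in some items, a '1' indicates no impact on your quality of life, while in others, a '1' signifies a significant impact", and add that 7 carries the opposite meaning to 1 on each item.

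The scoring rule follows in the same paragraph: "Nausea scores, vomiting scores, and total scores were calculated by summing responses across categories and the total number of responses".

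The printed anchors also show two directions. Thirteen items carry the label "Not very large at all", which reads as not at all under 1 and very large under 7. Items 3, 6, 11, 15 and 18 carry "Very large, not at all", which reads the other way round.

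The Protocol does not mention reversing any item, which way the final score points, its range, or a scoring manual. Section 3.7 (Statistical Analysis) does not cover the FLIE.

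**The concern.** A sum is a meaningful scale score only if every item points the same way. Appendix II says that the items do not, and then gives a sum with no alignment step. Someone who follows the appendix literally would add items that rise with impact to items that fall with it. That compresses the scores, gives a patient with no impact different values on the two nine-item domains, and moves the score the wrong way when a patient worsens on the opposite items.

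The FLIE is a named endpoint. Section 1.1 cites a possible quality-of-life benefit in the delayed and super-delayed phases as part of the case for the drug. With 60 subjects per group, avoidable attenuation of this comparison is worth removing.

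**Working it through.** The Protocol states no FLIE range, cut-off, standard deviation or power, so there is no figure of its own to reproduce.

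**Inputs.** From Appendix II: 18 items, 9 per domain, responses 1 to 7, mixed directions. From the printed anchors: opposite items 3 and 6 (nausea) and 11, 15 and 18 (vomiting). Assumed, not in the Protocol: inter-item correlation ρ from 0.3 to 0.7.

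**Step 1: span of the literal sum.** Let x be the impact on an item, from 1 (none) to 7 (maximum). A forward item records x and an opposite item records 8 − x.

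- Nausea (7 forward, 2 opposite): no impact 7×1 + 2×7 = 21; maximum 7×7 + 2×1 = 51.
- Vomiting (6 forward, 3 opposite): no impact 6×1 + 3×7 = 27; maximum 6×7 + 3×1 = 45.
- Total: no impact 21 + 27 = 48; maximum 51 + 45 = 96.

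| Score | Literal range | Literal span | Aligned range | Aligned span | Span kept |
|---|---|---|---|---|---|
| Nausea | 21–51 | 30 | 9–63 | 54 | 56% |
| Vomiting | 27–45 | 18 | 9–63 | 54 | 33% |
| Total | 48–96 | 48 | 18–126 | 108 | 44% |

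**Step 2: movement in the wrong direction.** A patient who goes from no impact to maximum impact on items 11, 15 and 18 only, with the other items unchanged, drops 3×6 = 18 points on the literal vomiting score.

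**Step 3: standardised effect.** Lost span overstates lost information, because the noise shrinks too. Assume m items of unit variance with common correlation ρ after alignment and the same treatment shift on each. With k items left reversed, the signal is proportional to m − 2k and the variance is (m − 2k)²ρ + m(1 − ρ). The retained effect is

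[(m − 2k)/√((m − 2k)²ρ + m(1 − ρ))] ÷ [m/√(m²ρ + m(1 − ρ))].

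- Vomiting (m = 9, k = 3), ρ = 0.3: (3/√9) ÷ (9/√30.6) = 1 ÷ 1.627 = 0.615. ρ = 0.7: (3/√9) ÷ (9/√59.4) = 1 ÷ 1.168 = 0.856.
- Nausea (m = 9, k = 2), ρ = 0.3: (5/√13.8) ÷ (9/√30.6) = 0.83. ρ = 0.7: (5/√20.2) ÷ (9/√59.4) = 0.95.
- Total (m = 18, k = 5), ρ = 0.3: (8/√31.8) ÷ (18/√109.8) = 0.83. ρ = 0.7: (8/√50.2) ÷ (18/√232.2) = 0.96.

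Squaring gives the equivalent share of sample retained. The loss is about 27% to 62% for vomiting and about 9% to 32% for nausea and the total.

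**Step 4: dependence on the item list.** The span kept is |m − 2k|/m. For the 18-item total this is 89% with one opposite item, 44% with five and 0% with nine. A nine-item domain always keeps at least 1/9.

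**The case against.** The strongest reply is that the appendix never says the responses are left unrecoded. It speaks only of summing responses, in a visibly machine-translated sentence. Reversing items of a named questionnaire is the kind of detail a statistical analysis plan or scoring manual usually supplies, and the plan may exist although it is not shown. The instructions also show that the authors knew the directions differ.

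Part of this stands: it cannot be claimed that the sponsor intends to sum unaligned items. But the Protocol is not silent on scoring. It states a rule, and that rule does not fit the instrument described in the same paragraph. An analysis plan that recoded would be adding a step that the written rule does not contain.

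Two further points stand. The anchor labels are run together and translated, so the list of five items is a reading of damaged text. The instructions establish the mixed direction independently, but not the number of opposite items or their split of two and three. Also, the effect on the vomiting domain is the worst of the three and should not be quoted alone.

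A reader might infer that high and low impact cancel and that the FLIE scores are therefore invalid. The documents do not support this. On the anchors as read, 33% to 56% of the span remains, and a patient whose impact is uniformly worse still scores higher. The harm also arises only if nobody recodes, which the Protocol does not say.

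**Conclusion.** The point holds as a defect in a stated scoring rule: Appendix II gives a plain sum for items it describes as running in different directions, with no alignment step and no score direction. Followed literally, the rule distorts and attenuates the scores. Vomiting is affected most, and nausea and the total less.

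The spans depend on items 3, 6, 11, 15 and 18 being the opposite ones. The effect-size figures depend also on the assumed correlations and on an equal treatment shift across items.

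Severity is moderate. One secondary endpoint is affected; the primary endpoint, the sample size and the safety analysis are not. Item responses can still be recoded at analysis.

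**What to change.** Add to Appendix II that the opposite-direction items are recoded as 8 minus the response before any summing. List those items by number after checking the original printed form (provisionally 3, 6, 11, 15 and 18). State that higher scores then mean more impact, with ranges of 9–63 per domain and 18–126 in total. If the sponsor prefers higher scores to mean less impact, the other thirteen items are recoded instead and the ranges are unchanged. Any analysis plan should repeat the same rule.

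The cost is a sentence or two of text and one line of code, with no new data. It should be settled before any FLIE scores are computed, including for the interim analysis if they are used there.
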